	hypoglycaemia; thereafter further insulin adjustments may be implemented as necessary. For further details see Section 4.2.1
G	An early End of Treatment (eEOT) Visit, as well as a Follow-up Visit 12, should be performed for any patient who discontinues study medication prematurely; the eEOT
	Visit should be completed as soon as possible after study medication is stopped.
	the 9-point plasma glucose profile should only be performed if it is feasible for it to be done over a 24 hour period before the eEOT visit
	when study medication is still being taken; otherwise it can be omitted. Visit 12 should be performed 3 weeks after the eEOT visit, and where possible, patients should
	then be followed up according to the visit schedule. For further details see Section 6.2.3
Н	NF: non-fasting; F: fasting
I	Following the termination of trial medication, and if deemed necessary based on Investigator's judgement, additional support (e.g. telephone interaction) can be given to
	the patient during the adjustment of T1DM therapy in the Follow-up period
J	Safety laboratory includes calculation of the eGFR. Following a positive urine dipstick result (at the site) for leukocyte esterase (for WBC) or nitrite, a midstream urine
	sample for urine culture is triggered. For further details see Section 5.3.3
K	For female patients of child-bearing potential (local urine pregnancy test)
K	
_	
O	Home monitoring device: meter for monitoring of blood (plasma) glucose and ketone levels at home
P	Self-Blood Glucose Monitoring (SBGM) should be performed daily from the beginning of the T1DM therapy optimisation period to the end of the Follow-up period.
	Measurements should be taken 4 times a day as a minimum e.g. at least before breakfast, lunch, dinner and bedtime. Additional measurements will also be warranted (e.g.
	after clinic Visit 6). For further details see Section 5.3.2.1. Ketone measurements should be performed by the patient in case of any symptoms of DKA. Other conditions
	may also trigger the need for ketone measurement. For further details see Section 5.3.2.2
Q	
R	For the screening visit (Visit 1) an abbreviated, safety laboratory and urinalysis will be performed as follows: liver transaminases, alkaline phosphatase, serum creatinine,
	TSH, and urinalysis. For further details see Section 5.3.3
S	At Visits 6, 11 EOT, eEOT (if applicable) and 12 only, the safety laboratory testing will include lipids. Samples should be obtained from the patient in a fasting state. For

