- iPTH (intact parathyroid hormone)⁴
- Sodium
- $TSH^{1,5}$
- Blood urea nitrogen (BUN)
- Uric acid

Lipids⁶

- Cholesterol (total)
- HDL cholesterol
- LDL cholesterol (calculated)
- Free fatty acids

- Apo A-1
- Apo B
- **Triglycerides**
 - o direct measurement of LDL cholesterol (reflex test if triglycerides are > 400 mg/dL or 4.52 mmol/L)
- At the screening visit (Visit 1), only the following parameters are part of the profile: liver transaminases, alkaline phosphatase, creatinine, and TSH
- C-peptide will only be assessed at Visit 2
- Cystatin C will only be assessed at Visits 6, 11 EOT, eEOT (if applicable) and 12
- iPTH will be only be assessed at Visits 6, 8, 11 EOT and eEOT (if applicable)
- TSH will only be assessed at Visit 1
- Lipids will only be assessed at Visits 6, 11 EOT, eEOT (if applicable), and 12

Page 55 of 122

Proprietary confidential information © 2016 Boehringer Ingelheim International GmbH or one or more of its affiliated companies

Table 5.3.3: 2 Laboratory parameters – urine

Semi-quantitative (dipstick) urinalysis		Quantitative urinalysis		
•	Nitrite ¹	•	Albumin	
•	Protein	•	Creatinine	
•	Ketones ³	•	Human chorionic gonadotrophin	
•	Urine pH		$(hCG)^2$	
•	Leukocyte esterase (for WBC) ¹			

Microscopic urinalysis

Microscopic analysis will be performed as a reflex test if any of the above semiquantitative (dipstick) tests except for ketones are abnormal:

- Urine RBC/erythrocyte
- Urine WBC/leukocytes¹
- Urine sediment microscopic examination

Urine culture

Urine culture will be triggered by positive leukocyte esterase (for WBC) and/or nitrite in the semi-quantitative test/dipstick. The culture will include an antibiogram

- Nitrite and leukocyte esterase (for WBC) will be determined both locally on site (not recorded in eCRF) and via the central laboratory. A positive result at site triggers the sampling of mid-stream urine for urine culture
- Urine pregnancy testing will be performed locally in female patients of child-bearing potential only according to the timepoints indicated in the Flow Chart
- At clinic visits where centralized safety laboratory tests are not planned, urine ketones will be determined only locally at the site.

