6.2.3.2 End of treatment - early discontinuations (eEOT) and withdrawals

For the analysis of this trial it is absolutely crucial that all planned assessments are done as planned, even if patients discontinue trial treatment. Patients who discontinue treatment prematurely and who do not withdraw their informed consent must therefore be followed up for the intended regular treatment period. All assessments related to the primary and secondary endpoints must be performed as if the patient would have remained on treatment.

Patients who discontinue study medication early should have the assessments for eEOT (Early Discontinuations Only) performed, as indicated in the Flow Chart. For such patients, the eEOT Visit should be done as soon as possible after the decision to discontinue has been made. If the eEOT Visit occurs within the time window of a scheduled visit and the patient continues to be followed up, the eEOT Visit will replace that scheduled visit. For example:

• if a patient discontinues study medication 16 weeks after randomisation (i.e. between Visits 9 and 10), the eEOT Visit could be scheduled one week later, and it would occur within the time window of the next scheduled visit (i.e. Visit 10 at Week 18 +/-7 days). When returning to the visit schedule, after completing the 3 week Follow-up Visit (see Section 6.2.3.3 below), the patient would return for Visit 11 EOT at Week 26

If a patient intends to immediately discontinue (withdraw) from the study, an eEOT Visit should be performed as soon as possible after the decision to withdraw has been made.

Proprietary confidential information © 2016 Boehringer Ingelheim International GmbH or one or more of its affiliated companies

Patients who discontinue treatment prematurely (prior to 26 weeks) but continue to be followed up should be registered as "withdrawn from treatment" in the IRT system, whereas patients who withdraw from the trial should be registered as "withdrawn from study".

- eEOT should be done with the patient in a fasted state (i.e. no food or drink except water for 10 hours), and patients should be reminded to bring all used/unused medication with them to the visit. The patient should be reminded not to start any new anti-diabetic therapy until after Visit 12
- Patients should be reminded to continue with e-diary entries, checks of glucose and ketones using the glucose and ketone monitoring device for the remainder of the observation period

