 - 6.2.3.3 Follow-up visit (Visit 12) completers

Patients who successfully complete the 26 week treatment period should have the assessments for Visit 12 performed, as indicated in the Flow Chart. For these patients:

- Visit 12 should be done with the patient in a fasted state (i.e. no food or drink except water for 10 hours)
- The patient e-diary will be checked after which it should be removed from the patient, together with all other study-related devices and equipment, once Visit 12 is complete
 - 6.2.3.4 Follow-up visit (Visit 12) early discontinuations (eEOT) and withdrawals

For patients who discontinue treatment prematurely prior to completion of 26 weeks the following should be performed whenever possible once an eEOT Visit has been completed (see Section 6.2.3.2):

- 3 weeks after the date of the eEOT Visit, patients should complete Visit 12. Visit 12 should be done with the patient in a fasted state (i.e. no food or drink except water for 10 hours), and all assessments indicated in the Flow Chart for Visit 12 should be performed
- Thereafter, patients should be followed up according to the visit schedule (e.g. a patient who discontinued study medication a week after Visit 8 (Week 4) i.e. at Week 5 would next be followed up for Visit 9 (Week 12) after having completed an eEOT visit as soon as possible after Week 5, and a Visit 12 at Week 8.
- The Investigator may negotiate a revised visit schedule should the patient be unwilling or unable to adhere to the regular schedule according to the Flow Chart. These follow-up visits may occur by telephone or in the clinic but Visit 11 EOT (Week 26) must be performed as a clinic visit in order to complete all scheduled assessments
- When being followed up according to the visit schedule, only assessments relating to the primary and secondary endpoints and general safety have to be completed (i.e. weight, vital signs, physical examination, ECG, safety laboratory, pregnancy test, HbA_{1c}, e-diary completion,

c02993089-03 Trial Protocol Version 2.0 Page 73 of 122

Proprietary confidential information © 2016 Boehringer Ingelheim International GmbH or one or more of its affiliated companies

collection of AEs and changes in concomitant therapy). All other assessments are optional

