6.7 BASELINE, TIME WINDOW, AND CALCULATED VISITS

With regard to efficacy and safety endpoints, the term "baseline" refers to the last observed measurement prior to administration of any randomised study medication. For specific endpoints, baseline definitions are as follows:

Serum beta-hydroxybutyrate (BHB)

- Serum BHB sampled at the site and analysed at the central laboratory

Baseline will be defined as the fasted measurement observed at Visit 6, before first drug intake.

- Capillary patient self-measured BHB via the ketone meter and reported in the diary

For the analysis on morning or daily measurements (see [Section 7.8.2.5](#)), baseline will be defined as the mean of morning or daily measurements reported during the run-in period, respectively (Visit 5 to Visit 6, including the day of first administration of trial drug).

[REDACTED]

Hypoglycaemia rate

The event rate of hypoglycaemia (using the respective endpoint definition) during the 4 weeks prior to randomisation (from Day -28 up to Day -1). Collapsing will be performed as per the rules in Sections [5.4.6.3](#) and [5.4.7](#). Rates will be presented per 30 days and also per patient year.

Insulin dose (total daily, total daily basal or total daily bolus)

Mean daily insulin requirement during the run-in period (Visit 5 to Visit 6, excluding day of randomisation). If < 4 days of valid insulin data is reported during the run-in period then the measurement will be considered missing. For data handling rules see [Section 5.4.6.2](#).

[REDACTED]

[REDACTED]

[REDACTED]

[REDACTED]

[REDACTED]

Table 6.7: 1 Endpoint specific follow-up period for the assignment to active treatment

Endpoint	Last day of assignment to treatment phase (days after study drug stop date)
Efficacy	
HbA _{1c}	7
FPG	1
MDG	1
CGM	*
Body weight	1
Blood pressure	1
Waist circumference	7
Insulin dose	0
Hypoglycaemia	1
UACR	1
Health economics and QoL	1
Safety	
Adverse events	7
Hypoglycaemia ^[1]	1
Hepatic injury ^[2]	30
Safety laboratory measurements	3
AST/ALT/TBL ^[3]	30
Pulse rate	1

*Refer to [Section 5.4.4](#) for the assignment of CGM measurements to the on-treatment period

[1] Refer to all hypoglycaemia analyses except the general hypoglycaemia AE analysis by SOC and PT.

[2] Refer to a sensitivity analysis including all hepatic injuries with an onset date up to 30 days after the study treatment stop (see Section 7.8.1.4).

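### The worked example in Protocol 6.2.3.2 permits an early end-of-treatment visit 7 days after the last dose, too late under the SAP for on-treatment blood pressure, lipids and cystatin C

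*Protocol*

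**What the plan says.** The general rule is promptness. Flow Chart footnote G says of the eEOT that the "Visit should be completed as soon as possible after study medication is stopped", and Protocol 6.2.3.2 asks for the same once the decision to discontinue is made. Neither gives a maximum number of days.

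Section 6.2.3.2 adds that an eEOT falling inside a scheduled visit's window replaces that visit. It illustrates this with a patient who stops at Week 16, for whom "the eEOT Visit could be scheduled one week later, and it would occur within the time window of the next scheduled visit", namely Visit 10 at Week 18 +/-7 days. Section 6.2.3.4 has a second example, a stop at Week 5, with "an eEOT visit as soon as possible after Week 5, and a Visit 12 at Week 8".

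Two groups of laboratory tests have a sparse schedule (footnotes to Protocol Table 5.3.3: 1): "Lipids will only be assessed at Visits 6, 11 EOT, eEOT (if applicable), and 12", and "Cystatin C will only be assessed at Visits 6, 11 EOT, eEOT (if applicable) and 12".

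SAP Table 6.7: 1 sets how long after the stop date a value still counts as on-treatment: 1 day for blood pressure, body weight and FPG, 3 days for safety laboratory and 7 days for HbA1c and adverse events. Later values are off-treatment. Footnote A to SAP Table 6.7: 2 applies these limits to the eEOT, with the last day included. SAP 7.8.2 repeats the 3-day rule and admits a patient to the analysis of a laboratory parameter only if at least one on-treatment value exists.

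**The concern.** A site that follows the 6.2.3.2 example waits a week to merge two visits. By then every eEOT measurement with a 1-day or 3-day limit has become off-treatment. For most parameters an earlier visit covers the gap. For lipids and cystatin C nothing does: in a patient who stops early, the eEOT is the only scheduled draw after baseline that can be on-treatment.

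Lipid change is a named safety endpoint (SAP 5.4.9, nine measures), and Protocol 1.2.3.1 reports small cholesterol increases with the drug in T2DM. Early stoppers are a group one would not want to drop from an on-treatment safety analysis through scheduling alone.

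**Working it through.** **1. The example's own arithmetic.** The SAP counts planned days from 0 and the Flow Chart counts randomisation as Day 1.

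- Stop at Week 16: 16 x 7 = SAP day 112, study day 113.
- eEOT one week later: SAP day 119, study day 120.
- Visit 10 window: 126 +/- 7 = SAP days 119 to 133; 127 +/- 7 = study days 120 to 134.

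The example reproduces. The eEOT lands on the first day of the Visit 10 window, 7 days after the stop.

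**2. The 7-day gap against SAP Table 6.7: 1.**

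| Measure | Limit (days) | Gap minus limit | Status |
|---|---|---|---|
| Blood pressure | 1 | 6 | off-treatment |
| Body weight | 1 | 6 | off-treatment |
| FPG | 1 | 6 | off-treatment |
| Safety laboratory | 3 | 4 | off-treatment |
| HbA1c | 7 | 0 | on-treatment, no slack |

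**3. Which measures actually lose an on-treatment value.** This uses the Flow Chart schedule and the SAP 6.7 windows.

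- *Blood pressure.* The Week 18 window is days 106 to 154 (SAP Table 6.7: 3) and contains both 112 and 119. A prompt eEOT gives one on-treatment Week 18 value; the example gives none.
- *HbA1c.* Same Week 18 window (Table 6.7: 2). The value is kept either way.
- *Weight.* Not scheduled at Visit 10. The midpoint rule gives a Week 12 window from (28 + 84)/2 + 1 = 57 to (84 + 182)/2 = 133. Visit 9 (day 84) lies in it and normally supplies the value.
- *FPG.* Scheduled after baseline only at Visits 9 and 11 EOT (plus eEOT and Visit 12). The Week 12 window again ends at day 133, and Visit 9 normally supplies the value.
- *Routine chemistry.* The Visit 9 value remains. The eEOT set is lost as the last on-treatment value.
- *Lipids and cystatin C.* Visits 8 and 9 do not include them. For a Week 16 stop, Visit 11 EOT is 26 - 16 = 10 weeks after the stop, and Visit 12 comes 3 weeks after eEOT. Both are beyond 3 days. On-treatment values after baseline: one with a prompt eEOT, none in the example.

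**4. Consequence.** Without an on-treatment value the patient is excluded for that parameter under SAP 7.8.2. LOCF does not help, because SAP 6.6.1.5 does not carry baseline forward. The patient leaves the lipid OC and LOCF tables (SAP 7.8.2.3) and the creatinine-cystatin C eGFR shift tables (SAP 7.8.2.4).

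For the Week 26 lipid ANCOVA the SAP prints no lipid window. Applying its midpoint rule, the Week 26 window starts at day 2 (following the pattern of Table 6.7: 2) or at 182/2 + 1 = 92. Day 112 is inside on either reading, so a prompt eEOT value would enter the ANCOVA and the 7-day value would not.

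**5. The other example.** In 6.2.3.4, Visit 12 at Week 8 is 3 weeks after eEOT, so eEOT is at about 8 - 3 = Week 5, the week of the stop. That example has almost no lag; the one in 6.2.3.2 has 7 days.

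**The case against.** The strongest reply is that promptness is the operative rule and is stated repeatedly. The 6.2.3.2 example illustrates visit replacement, is worded as a possibility, and is balanced by the example in 6.2.3.4. All of this is correct. A reader might infer that the protocol instructs sites to wait a week; it does not. What remains is that one of its two examples shows a wait and ties it to saving a visit.

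A reader might also infer that weight and FPG results suffer because their limit is 1 day too. In the example they lose no visit value, since Visit 9 normally supplies it. Carrying the same delay over to Visit 9 would remove more, but neither document describes that case.

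The blood pressure loss is one intermediate value. Weeks 1, 4 and 12 are already in the model, the confirmatory contrast is at Week 26 (SAP 7.5.1.4), and the off-treatment value stays in the all-data displays. The lipid and cystatin C outputs are safety analyses outside the confirmatory testing (Protocol 7.3.4). Liver enzyme elevations have a supplementary 30-day analysis (SAP 7.8.2.2). These facts limit the size of the point.

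The protocol (21 Oct 2016) predates the SAP (17 May 2017), so its authors did not have these limits in print. That explains the mismatch but does not remove it.

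Finally, one merged visit spares a patient who must be retained to Week 26. This has some weight, and the cost is counted under the fix.

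**Conclusion.** The point holds as a minor one. For a patient handled as in the 6.2.3.2 example, compared with a prompt eEOT, on-treatment Week 18 blood pressure values go from 1 to 0, post-baseline lipid sets from 1 to 0 and post-baseline cystatin C values from 1 to 0. HbA1c is kept with no days to spare. The delay brings no analytical gain, since SAP days 112 and 119 share the Week 18 window.

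This assumes that a site follows the example and that no unscheduled on-treatment value exists. The ANCOVA part further assumes that the midpoint rule applies to lipids; the exclusion under SAP 7.8.2 does not depend on it.

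A reader might infer a threat to the primary result. The documents do not support that: a day-7 HbA1c is still on-treatment, the primary contrast is at Week 26, and the effectiveness analysis uses off-treatment values as well. Adverse events keep their 7-day window. How many patients would be scheduled this way cannot be computed. The 6% allowance in Protocol 7.7 is for patients who do not qualify for the FAS and is not a discontinuation rate.

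**What to change.** Replace the 6.2.3.2 example with one where a prompt eEOT happens to fall in a window. For instance: a patient stops at Week 17 (study day 120) and has eEOT the next day (day 121); this lies within Visit 10's window of days 120 to 134 and replaces Visit 10; after the 3-week follow-up visit the patient returns for Visit 11 EOT at Week 26.

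Add one sentence: eEOT must not be postponed to coincide with a scheduled visit; it should take place on the day of the last dose or the next day, otherwise within 3 days where possible and preferably no later than 7 days; a later eEOT is still performed.

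Leave the SAP windows as they are. Protocol 3.2 puts the pharmacodynamic effect at about three days after the last dose, so wider windows would label washout values as on-treatment.

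The cost is protocol wording and a site reminder. Under the order in 6.2.3.4 (eEOT, then Visit 12, and "Thereafter, patients should be followed up according to the visit schedule"), a Week 16 stop means attendances at Weeks 16, 19 and 26 instead of 17, 20 and 26: three either way. The prompt eEOT still supplies Week 18 HbA1c and blood pressure. One extra attendance arises only if a site also holds Visit 10 separately.

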Based on the mode of action of empagliflozin and the results of previous trials in T1DM (for further details see Section 1), at randomisation on Day 1 (Visit 6) and the initiation of randomised study medication, for patients with an HbA_{1c} of 7.5 to < 8% at Visit 5, Investigators are advised to reduce the patient's total insulin dose by 10% to avoid hypoglycaemia. For patients with an HbA_{1c} of \geq 8% at Visit 5, Investigators are advised to adjust the patient's total insulin dose based on need as assessed by frequent SBGM and close patient follow-up upon initiation of randomised study medication. In all cases, the actual reduction will be dependent upon individual glucose values. Thereafter and until the end of the trial (Visit 12), further adjustments to insulin therapy (both basal and bolus insulin) may be implemented as necessary to avoid hypoglycaemia and also hyperglycaemia to keep ensuring that, in the Investigator's opinion, the patient is achieving the best standard of care in accordance with local guidelines.

Apart from the recommendation for an initial insulin reduction as mentioned above at the start of randomised treatment, there will be no protocol-defined algorithm towards insulin adjustment in this trial. However, the Sponsor will provide additional support to the Investigator with respect to insulin adjustment via training documentation that will be presented at Investigator Meetings and made available in the ISF. Throughout the trial, adjustment needs to balance a patient's individual risk for hypoglycaemia on the one hand and the risk for hyperglycaemia and DKA on the other hand with special caution at the beginning of the treatment period, and in the Follow-up period, when empagliflozin treatment

Page 42 of 122

Proprietary confidential information © 2016 Boehringer Ingelheim International GmbH or one or more of its affiliated companies

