• Visit 11 EOT at 26 weeks will be the last visit for these patients, since Visit 12 will already have been completed 3 weeks after the eEOT Visit as explained above. At Visit 11 EOT therefore, the patient e-diary will be checked after which it should be removed from the patient, together with all other study-related devices and equipment, once the visit is completed

For patients who discontinue treatment prematurely and do not wish to follow the visit schedule, at least a contact should be planned, at the timepoint of the primary endpoint at 26 weeks to collect data about the vital status as a minimum.

If study treatment is stopped prior to completion of 26 weeks and the patient intends to immediately discontinue (withdraw) from the study, an eEOT Visit should be performed as soon as possible after the decision to withdraw has been made. The patient should return for a Visit 12 (3 weeks after the eEOT). At this visit all assessments should be performed according to the Flow Chart.

Page 74 of 122

Trial Protocol Version 2.0

Proprietary confidential information © 2016 Boehringer Ingelheim International GmbH or one or more of its affiliated companies

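### For early stoppers who stay in follow-up with an eEOT after about Week 23, Protocol 6.2.3.4 makes Visit 11 EOT the last visit on a premise that is false and contradicts the three-week Visit 12 rule

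*Protocol*

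**What the plan says.** Protocol Section 6.2.3.4 opens with a broad scope: "For patients who discontinue treatment prematurely prior to completion of 26 weeks the following should be performed whenever possible". Its first instruction is "3 weeks after the date of the eEOT Visit, patients should complete Visit 12", and only after that does the patient return to the regular schedule. Flow Chart footnote G gives the same order.

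The section then states, with no exception for late stops: "Visit 11 EOT at 26 weeks will be the last visit for these patients, since Visit 12 will already have been completed". It draws a consequence from this: at Visit 11 EOT the e-diary is checked and "should be removed from the patient, together with all other study-related devices and equipment, once the visit is completed".

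Other current text ties the end of participation and of home monitoring to Visit 12:
- Section 3.1 has all patients enter a three-week follow-up and ends participation at Visit 12.
- Sections 5.2.3 and 5.3.2.1 supply the e-diary and the glucose meter to all patients until Visit 12. Section 5.3.2.2 describes a glucose meter that also measures ketones.
- Flow Chart footnote P says: "Self-Blood Glucose Monitoring (SBGM) should be performed daily from the beginning of the T1DM therapy optimisation period to the end of the Follow-up period".
- Section 4.2.1 asks that insulin adjustment balance hypoglycaemia against hyperglycaemia and DKA "with special caution at the beginning of the treatment period, and in the Follow-up period, when empagliflozin treatment" is started and stopped.

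Patients who leave the study altogether have a separate paragraph in 6.2.3.4, which asks them back for Visit 12 three weeks after eEOT.

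**The concern.** The last-visit sentence rests on a matter of dates: that Visit 12 always precedes Week 26. This is true for early stops and false for late ones, yet the rule and the device return that follows from it carry no limit.

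At stake are Visit 12 itself (safety laboratory, ketones, vital signs, AE check) and home glucose and ketone monitoring in a period that the protocol singles out for caution. Section 3.2 justifies the three weeks partly by the wish to see whether unexpected side effects reverse. The SAP also uses post-treatment data: change in haematocrit to follow-up (7.8.2.1), serum BHB in follow-up (7.8.2.5), and hepatic events up to 30 days after the last dose (7.8.1.4).

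The literal text also has an odd result. A patient who stops at Week 25 and stays in the study would be closed out after about 7 days, while one who withdraws from the study is asked back at 21.

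**Working it through.** **Inputs.** Visit 11 EOT is Day 183 with a window of ±3 days, and Visit 12 has a window of ±7 days (Flow Chart). Visit 12 is due at eEOT + 21 days (6.2.3.4; footnote G). An eEOT inside the window of a scheduled visit replaces that visit (6.2.3.2).

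**The plan's own figures.** The 6.2.3.4 example has eEOT at about Week 5 and Visit 12 at Week 5 + 3 = Week 8, as stated. For completers, 183 + 21 = Day 204, the Flow Chart day for Visit 12. The 6.2.3.2 example stops at Week 16 with eEOT at Week 17, so Visit 12 falls at Week 17 + 3 = Week 20, well before Week 26. Both examples are early enough for the stated order to work. The protocol gives no late example.

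**Nominal cut-off.** The premise needs eEOT + 21 ≤ 183, so eEOT ≤ Day 162, which is Week (162 − 1)/7 = 23.

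| eEOT | Visit 12 due | Relative to Day 183 | Days from eEOT to Day 183 |
|---|---|---|---|
| Day 155 (Week 22) | Day 176 | 7 days before | 28 |
| Day 162 (Week 23) | Day 183 | same day | 21 |
| Day 163 | Day 184 | 1 day after | 20 |
| Day 169 (Week 24) | Day 190 | 7 days after | 14 |
| Day 176 (Week 25) | Day 197 | 14 days after | 7 |
| Day 179 | Day 200 | 17 days after | 4 |

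**With the windows** (assuming that ±7 days also applies when Visit 12 is dated from eEOT):
- Most lenient: Visit 12 a week early and Visit 11 EOT three days late. eEOT + 14 ≤ 186 gives eEOT ≤ Day 172.
- Strictest: Visit 12 a week late and Visit 11 EOT three days early. eEOT + 28 ≤ 180 gives eEOT ≤ Day 152.
- For eEOT on Days 173 to 179 the earliest Visit 12 is Days 187 to 193, after the latest Visit 11 EOT on Day 186. The written order is then impossible.
- From Day 180 (183 − 3) the eEOT replaces Visit 11 EOT, so Visit 12 necessarily comes later.

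**Residual effect period.** Section 5.3.7 counts AEs as on treatment for 7 days after the last dose. Since 176 + 7 = 183, a last dose after Day 176 has a residual effect period that runs past Visit 11 EOT on Day 183.

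**The case against.** The strongest reply is that the protocol, read as a whole, still requires Visit 12. Sections 3.1, 5.2.3, 5.3.2.1 and 6.2.3.4 and footnote G all say so, Section 6.2.3.2 continues diary and ketone checks for the rest of the observation period, and the last-visit sentence gives a reason which, once it fails, leaves the rule without a basis. A site could hold Visit 11 EOT at Week 26 and Visit 12 afterwards, the order completers follow. This stands in part. A reader might infer that follow-up and ketone monitoring do end early for everyone who stops after Week 23. The documents do not establish that; they show a conflict that sites could resolve differently. Nor does the point cover study withdrawers, or every eEOT between Days 163 and 172, where the windows may still allow the stated order.

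Three further inferences also fail:
- **Week 26 HbA1c is lost.** The SAP's Week 26 HbA1c window opens at day 155 (Table 6.7: 2), and off-treatment values are assigned to visits in the same way. A visit a few days late is a schedule deviation, not shown to be lost data.
- **AE follow-up is cut off or not comparable with completers.** Section 5.3.7 requires AEs to be followed until resolved or sufficiently characterised, even after trial completion. Visit 11 EOT itself includes safety laboratory, ketones and an AE check. Post-treatment AEs are assigned separately from on-treatment AEs, and off-treatment follow-up of early stoppers already varies widely by design.
- **About 9% of stops are affected.** Days 163 to 179 are 17 of about 182 treatment days (9.3%). That is a share of calendar days, and a share of patients only if stops are spread evenly, which no document says.

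The allowances in 6.2.3.4 for what is possible, and for a negotiated schedule when a patient is unwilling or unable to attend, do not answer the point. Neither qualifies the last-visit and device-return sentences.

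**Conclusion.** The point holds as an internal contradiction. For patients who stop treatment early, stay in follow-up and have an eEOT after about Week 23, the stated reason for making Visit 11 EOT the last visit is false: nominally after Day 162, and without remedy inside the windows for Days 173 to 179. The sentence also conflicts with the three-week Visit 12 rule, with participation ending at Visit 12, and with diary and meter use until then.

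The possible consequence, only where a site follows the sentence literally, is a dropped Visit 12 and home monitoring cut from 21 days after eEOT to between 4 and 20 (eEOT on Days 163 to 179). The cut-off follows the eEOT date, not the stop date; if the eEOT is delayed, the corresponding stop date is earlier. The documents do not say how many patients fall in this range, and the number is probably small. A correction is worthwhile because it is cheap and concerns post-treatment safety observation.

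**What to change.** In Section 6.2.3.4, limit the last-visit sentence and the device-return sentence to patients whose Visit 12 has in fact been completed by Visit 11 EOT. For later eEOT visits, including those that replace Visit 11 EOT, reconcile the order of the two visits, which one is last, and when the e-diary and meter are returned, with Flow Chart footnotes G and P and with Sections 3.1, 5.2.3 and 5.3.2.1. A worked example of a late stop beside the existing early ones would help sites. How to reconcile the passages is for the sponsor to decide; no clinical rule is proposed here.

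The cost is one or two sentences and a matching Flow Chart footnote. At most it adds one visit for a few late stoppers, which 6.2.3.4 already calls for. No analysis needs to change.
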